### **Study protocol**

In an online survey, participants will be asked to imagine a new U.S. policy which would require prisons to serve meals that meet the government definition of healthy. In a between-subjects experiment, participants will be randomly assigned to view 1 of 3 different rationales for the new policy—public safety, right-to-health, or cost-saving—or be assigned to a control arm where no rationale is given. After viewing the rationale, participants will be asked whether they would strongly support, somewhat support, neither support or oppose, somewhat oppose, or strongly oppose the policy. Participants will also answer demographic questions.

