#### **Statistical methods**

Using linear regression, we will regress policy support on indicator variables for the experimental arm, excluding the control arm as referent. In this model, policy support will be treated as a continuous variable with responses ranging from 1 (representing strongly oppose) to 5 (strongly support). Analyses will estimate average differential effects (ADE, differences in predicted means) for each rationale compared to the control. We will use a two-sided critical alpha of 0.05 to conduct all statistical tests. All confidence intervals presented will use a 95% confidence level. We will then use pairwise comparisons to compare the predicted outcomes for each rationale to one another, using Bonferroni-Holm corrected p-values, to adjust for these 3 additional post-hoc tests.

We will use linear regression to examine correlates of policy support. We will regress policy support on the following demographic characteristics in a multivariable model:

- Reason for policy (experimental arm, with control arm as referent)
- Age
- Gender
- Race/ ethnicity
- Income
- Education
- Political party affiliation
- Having prior interactions with the criminal legal system
- Holding biases toward people who are incarcerated

For all analyses, we will exclude participants who complete <90% of the survey or who complete the survey implausibly quickly (defined as <1/3 of the median completion time).

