### **Sample size needs**

This study will occur as an auxiliary study to an experiment examining the impact of nudges on improving the healthfulness and environmental sustainability of grocery purchases (i.e., the parent study). The total sample size (~1,200 participants) was calculated based on the anticipated effect sizes in the parent study.

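### Does entering bias toward incarcerated people beside the experimental arm in the correlates model spoil the estimates of the rationale effects?

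*SAP*

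**What the plan says.** The section Statistical methods sets out two regressions. In the first, "we will regress policy support on indicator variables for the experimental arm, excluding the control arm as referent". The same paragraph gives the estimand: "Analyses will estimate average differential effects (ADE, differences in predicted means) for each rationale compared to the control". The Holm-corrected comparisons between rationales follow from there.

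A new paragraph opens the second regression with its own aim: "We will use linear regression to examine correlates of policy support". It continues: "We will regress policy support on the following demographic characteristics in a multivariable model". The list starts with "Reason for policy (experimental arm, with control arm as referent" and ends with "Holding biases toward people who are incarcerated".

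On order, the section Study protocol places the support question after the rationale and adds only this: "Participants will also answer demographic questions". The SAP does not say when the bias item is asked, and it does not say how the arm coefficients of the second regression are to be read.

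**The concern.** Age, education and race cannot be changed by reading a sentence about prison meals. An attitude toward incarcerated people can, and a right-to-health or public-safety rationale speaks to it directly. If bias is measured after the rationale, it may lie on the path from rationale to support. Adjusting for it then removes part of the effect. If some unmeasured attitude drives both bias and support, it also brings in a further distortion.

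The output would contain a second set of rationale-versus-control coefficients, under a heading that calls the covariates demographic. A reader could set these beside the average differential effects and put any gap down to adjustment for background characteristics, when it came from conditioning on something the rationale had changed. The bias coefficient would likewise describe an attitude measured after exposure, not a pre-existing trait.

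**Working it through.** The SAP gives no figure to reproduce here. Its sample size ("The total sample size (~1,200 participants") comes from the parent study, with no effect size, SD or power stated. The check is therefore algebra plus assumed ranges.

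**Inputs**
- From the SAP: about 1,200 participants, four arms, support scored 1 to 5.
- Assumed: equal allocation (1,200 / 4 = 300 per arm); outcome SD 1.0 to 1.4; shift in bias by arm, a, from -0.2 to +0.2 SD; bias coefficient, b, from -0.3 to -0.5 points per SD.

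**Size of the gap.** In least squares, with the same other covariates in both models:

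arm coefficient with bias - arm coefficient without bias = -a × b (fitted values)

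- a = 0: gap 0.
- a = -0.2, b = -0.5: -(-0.2 × -0.5) = -0.10 points.
- a = +0.2, b = -0.5: -(0.2 × -0.5) = +0.10 points.
- Add an unmeasured attitude correlated 0.5 with bias and worth -0.3 points on support. The fitted bias coefficient becomes -0.5 + 0.5 × (-0.3) = -0.65, and the gap is ±0.2 × 0.65 = ±0.13 points.
- The same attitude with the opposite sign gives -0.5 + 0.5 × 0.3 = -0.35, and a gap of ±0.07.

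Large simulations agree. For a = -0.2, b = -0.5 and no shared attitude, the coefficient is 0.197 without bias in the model and 0.097 with it. With the -0.3 shared attitude it is 0.201 and 0.071.

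**Scale.** The standard error of a rationale-versus-control difference is SD × √(2/300):

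| Outcome SD | SE | 0.10 / SE | 0.13 / SE |
|---|---|---|---|
| 1.0 | 0.082 | 1.2 | 1.6 |
| 1.2 | 0.098 | 1.0 | 1.3 |
| 1.4 | 0.114 | 0.9 | 1.1 |

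This is only a rough yardstick, because both coefficients come from the same participants and are correlated.

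**Wider assumptions.** Take a total effect of 0.25 points and a shift of -0.3 SD. The gap is then 0.3 × 0.5 = 0.15 points, or 0.15 / 0.25 = 60% of the effect. A stronger common cause (which adds -0.25 to the fitted bias coefficient) gives 0.3 × 0.75 = 0.225, leaving about 0.03 of the 0.25. So the gap could be large, and the SAP fixes neither its size nor its sign. The verdict therefore cannot rest on the gap being small.

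**Which planned results are affected, by scenario**

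| Bias item | Arm coefficients, arm-only model | Arm coefficients, correlates model |
|---|---|---|
| Asked before the rationale | Total effect | Total effect |
| Asked after, not moved | Total effect | Total effect on average |
| Asked after, moved | Total effect | Differ by -a × b |

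In simulations of 1,200 participants with a true total of 0.25, the arm-only model returned 0.24 to 0.26 in every scenario. Only the last cell of the table is a problem, and it belongs to the model that the SAP does not use for the rationale effect.

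**Would a check of bias by arm help?** At 300 per arm its 95% confidence interval has half-width 1.96 × √(2/300) = 0.160 SD. Its power is Φ(0.1/0.0816 - 1.96) = 23% for a 0.1 SD shift and Φ(0.2/0.0816 - 1.96) = 69% for 0.2 SD. It could not rule out the shifts considered here.

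**The case for a change.** The strongest case for a change is that the covariate list is SAP content, not a detail left to a questionnaire. The plan puts a movable attitude beside the randomised exposure, calls the set demographic, and places no limit on the use of the arm coefficients. The study description mentions the demographic questions after the rationale and the support item, which hints that bias may come late. Data have not been collected, so wording is cheap now.

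Part of this stands. The two variables are in one model, arm coefficients against control will be produced there, and no interpretive limit is written. If bias is asked late, its coefficient is a post-exposure association.

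The rest carries less weight. The order in which topics are mentioned is not a stated question order. The heading of the list is plainly loose, since experimental arm is on it too, so it does not show that the authors regard bias as a fixed trait. A correlates analysis claims association and no more, which is all the bias coefficient would have to support. The harm is a later misreading, not an analysis the SAP plans. Fitting further models and a bias-by-arm regression with 23% power at 0.1 SD would be out of proportion to that risk.

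**Conclusion.** No change to the plan is needed. Distortion requires two facts that the SAP does not establish: that bias is asked after the rationale, and that a rationale moves it. If both hold, the arm coefficients of the correlates model differ from the total effects by 0 to about 0.13 points in either direction for shifts of up to 0.2 SD. That is up to about 1.6 standard errors at SD 1.0, and more under larger assumed shifts. All of these inputs except the total sample size, the number of arms and the 1-5 scale are assumptions.

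The conclusion does not depend on that size. The SAP reads the rationale effects and the Holm-corrected comparisons from a regression on arm alone, where they are sound whatever the timing of the bias item. It never describes the arm coefficients of the correlates model as rationale effects. What is left is a point of interpretation that an analyst who knows the question order will handle when reporting the correlates table.

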### **Sample size needs**

This study will occur as an auxiliary study to an experiment examining the impact of nudges on improving the healthfulness and environmental sustainability of grocery purchases (i.e., the parent study). The total sample size (~1,200 participants) was calculated based on the anticipated effect sizes in the parent study.
